The aims of this study were two fold. First, this study was designed to test the effectiveness of NPWT with irrigation on wound healing and bioburden reduction. In addition, this study compared the wound healing and bioburden outcomes between saline or polyhexanide biguanide (PHMB) at low or high flow rates. A porcine model with dorsal full thickness excisional wounds was use for this study. The wounds were inoculated with *Pseudomonas aeruginosa* for 3 days prior to therapy initiation. Wounds were treated for 21 days of therapy with either NPWT, NPWT with simultaneous irrigation therapy using normal saline (Sal) or PHMB at low or high (Hi) flow rates, or control non-treated (Cont) wounds with dressings equivalent to the other groups. Data demonstrate that NPWT with either irrigation condition improved wound healing rates over control treated wounds, however did not differ from NPWT alone (Figure 1). When change in bioburden was compared to therapy day 0, NPWT improved bioburden in wounds over control therapy (Figure 2). The addition of saline or PHMB irrigation to NPWT further reduced bioburden over control and NPWT treated wounds. Both high and low flow rates resulted in similar decreases in wound bioburden. Together this is the first published controlled study demonstrating that NPWT with simultaneous irrigation therapy with either normal saline or PHMB has a positive effect on bioburden in a porcine model, which may translate clinically to improved wound healing outcomes.

[figure not shown]

Figure 1. Average change in wound area for each condition over time.

[figure not shown]

Figure 2. Average change in Pseudomonas levels for each condition over time.

Study 2

The Impact of Negative Pressure Wound Therapy with Instillation Compared to Negative Pressure Wound Therapy: A Retrospective Historical Cohort Controlled Study (Published in the Journal of Plastic and Reconstructive Surgery, 2013, Ref [94])

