This retrospective, historical, cohort-control study examined the impact of negative pressure wound therapy with and without instillation. One hundred forty-two patients (negative-pressure wound therapy, n=74; therapy with instillation, 6-minute dwell time, n=34; and therapy with instillation, 20-minute dwell time, n=34) were included in the analysis. The number of operative visits was significantly lower for the 6- and 20-minute dwell time groups compared with the non instillation group. Hospital stay was significantly shorter for the 20-minute dwell time group compared with the no-instillation group. Time to final surgical procedure was significantly shorter for the 6- and 20-minute dwell time groups compared with the no-instillation group. Percentage of wounds closed before discharge and culture improvement for Gram-positive bacteria was significantly higher for the 6-minute dwell time group (94 and 90 percent, respectively) compared with the no-instillation group. These results suggest that negative-pressure wound therapy with instillation (6- or 20-minute dwell time) is more beneficial than standard negative pressure wound therapy for the adjunctive treatment of acutely and chronically infected wounds that require hospital admission.

Innovation

This is the first prospective study to compare parameters of clinical efficacy of two different NPWT devices while also collecting information on direct and indirect treatment costs.

This is also the first clinical study that compares the clinical outcomes of NPWT and NPWT with simultaneous irrigation. Results will help clinicians develop treatment protocols to prescribe NPWT so treatment is optimized. This is also the first human study to measure the effect of NPWT and irrigation on bio-burden and wound healing. Our plan is to establish a treatment algorithm with saline irrigation solution based on bioburden reduction and acceleration of wound healing. This study will help determine how long it takes to eradicate bacteria with the goal of determining how long wounds typically need to be treated to “sterilize” the wound bed. Other objectives include determining whether eradication of wound bioburden enhances wound-healing rates with additional focus on the effects NPWT and NPWT with irrigation on a number of molecular and inflammatory markers.

Study Objectives and Design:

Study Groups and Design:

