The Cardinal Health NPWT PRO systems consist of powered suction pump components. The Cardinal Health NPWT PRO systems include a built-in placement holder for the 300cc and 500cc collection canisters. They have a pushbutton ON/OFF operation with five user-selectable pressure settings. The system produces optional pressure settings of -50mmHg, -75mmHg, -100mmHg, -125mmHg, and -150mmHg. It has alarms for Low Pressure/Leak, Full Canister, Low Battery and Therapy Timer. These alarms include both audible and visual indications. The system incorporates an IV pole hanger and bed hanger to make the product compatible with most clinical settings.

System Components

SpeedConnect Tubing

SpeedConnect is a single-lumen tubing set with adhesive flanges. The tube is kink-resistant and is 8 feet in length

Dressings

Black Foam Dressing

Hydrophobic, open-pore, reticulated foam with a high tensile strength is cut to fit the wound. The polyurethane foam dressings are provided in Small, Medium, Large, and XL sizes.

White Foam Dressing

Hydrophilic, high density foam dressing that is flexible when wet or dry.

Polyurethane Drape

Polyurethane drapes are provided in an 8" x 12" size and cover the wound and surrounding tissue.

Irrigation Tubing Set

Irrigation is supplied via a single-lumen tubing set with adhesive flanges and on end and an IV bag spike on the other end. The tube is kink-resistant and is 8 feet in length.

Canisters

The 300 cc and 500 cc single-patient use canisters collect exudate from the wound site. The canisters contain a porous polymer hydrophobic depth filter to prevent fluid ingress and gel packs to solidify wound exudate (300cc available with or without gel packs.) A red cap is included to prevent spillage upon disposal. Only 300 cc canisters are used in this study.

NPWT Operating Characteristics of Quantum NPWT Device	
Power Source	Electric/Battery
Mean Pressure	125mm Hg with continuous irrigation, normal saline 15 cc/hr
Mode	Continuous
Interface	Polyurethane Foam
Frequency of Interface Change	3x weekly

Control Devices: KCI USA, Inc. V.A.C. Ulta™ NPWT System & KCI USA, Inc. V.A.C. VIA™ NPWT System

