 - It is anticipated that most wounds will be determined ready for surgical wound closure by 4 weeks of therapy administration; however this may occur as early as after 2 weeks or subjects may be followed up to the full 12 weeks, and closure may occur anywhere inbetween (to be determined by investigator). It is also possible for some subjects that the wound may not be ready for closure even after 12 weeks. These subjects will be discharged from the study at that time and continue appropriate care for their wound with their physician.
 - The surgical wound closure procedure is performed in the operating room, using the most applicable of the following common mechanisms for closure, as is optimal for the individual subject and wound: delayed primary closure, rotational flap to close the wound, split thickness skin graft.
- Post Wound Closure Evaluation Phase
 - Following surgical closure of the wound, the subject will enter the post wound closure evaluation phase. This phase will last up to week 12 following study enrollment and therapy administration start, such that the duration of the post wound closure evaluation phase will vary for each subject according to the time point at which their wound was deemed ready for surgical closure. For example, a subject whose wound is surgically closed after week 4 of the therapy administration phase will enter a post wound closure evaluation phase that spans from week 5 through week 12, at which time the subject will exit the study. A subject whose wound does not close sufficiently for surgical repair by week 12 will exit the study at that time without entering the post wound closure evaluation phase.
 - The post wound closure evaluation phase will comprise weekly or standard of care evaluations in the outpatient clinic setting. If the wound remains closed with no sign of re-opening or infection, no further efficacy or safety evaluations will be taken at that visit. At post therapy

administration phase completion (as applicable to the individual subject), a standard of care blood draw will again be taken as at the baseline evaluation to assess lab markers.

- If at any of the post wound closure evaluation visits, the wound is found to have re-opened and/or shows signs of infection, the following will occur at the discretion of the physician:
 - Measurements of dehiscence will be taken
 - Surgical debridement of the wound will be done
 - NPWT only will be reapplied per standard of care

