Wound Assessment/ Debridement	X	X	X		X		
Tissue /bone ¹ / wound culture samples for qPCR cultures & bioburden analysis		X	X (Subsequent surgery)				

			while Inpatient)				
NPWT/NWPT (i) randomization/dressing application/changes		X	X	X (Weeks 2-4)	X (Weeks 2-4)		NWPT for maximum 4 weeks after baseline(Day0 surgery) if wound is not closed in the hospital
SF-36 Questionnaire	X					X	
Hyperspectral Imaging Analysis	X						To occur prior to surgery
Discharge Instructions			X		X		
Offloading			X	X	X		At hospital discharge & continuing to Week 12
Adverse Events		X	X	X	X	X	
Current/concomitant antibiotics	X	X	X	X	X	X	
Wound imaging/measurement		X	X		X	X	While active study wound is present
Neuropathy Disability Score in Patients with Diabetes	X						

¹ Only if performed as a necessary part of standard of care.

² Subjects who heal before week 12 will exit the study and complete EOS visit.

Biostatistics

Sample Size Justification:

There are no published data with the Cardinal PRO negative pressure wound therapy (NPWT) device with or without irrigation in order to determine an estimate of the sample size for this study. One of the purposes of this project is to obtain data, so we can power a larger multicenter study. Even though the KCI NPWT device with irrigation has been commercially available, there is little data about volume change or wound healing in the population we are studying.

The previous sample size justification was based on a comparison of the proportion of wounds expected to achieve surgical closure. The proportion of subjects with closed wound was 62% using traditional KCI NPWT and 94% using NPWT with periodic irrigations with Prontosan. For the sample size, we estimated 85-90% wound closure with NPWT with irrigation and 60% wound closure with NPWT without irrigation. We assume the NPWT devices (KCI and Cardinal) without irrigation would have similar results.

Equations

The following formula was used to estimate the required sample size, n , for the relative difference in proportions P_1 and P_2 .

$$n = \frac{\left(Z_{\alpha/2} \sqrt{2P(1-P)} + Z_{\beta} \sqrt{P_1(1-P_1) + P_2(1-P_2)} \right)^2}{(P_1 - P_2)^2}$$

where

$$P = \frac{P_1 + P_2}{2}$$

Using the formula above and assuming 90% wound closure with NPWT with irrigation and 60% wound closure with NPWT without irrigation and a type I error of 0.1, the required sample size is about 25. If a Type I error of 0.05 is assumed, then the required sample size is about 31.

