As the relative difference gets smaller, the required sample size increases. The two tables below show estimates for sample size for values of alpha of 5% and 10% for five values of P_2 .

P_1	P_2	rel. difference	$\alpha/2$	β	power	n
0.6	0.9	-0.75	.05	0.200	0.800	25
0.6	0.89	-0.73	.05	0.200	0.800	27
0.6	0.88	-0.70	.05	0.200	0.800	29
0.6	0.86	-0.65	.05	0.200	0.800	35
0.6	0.85	-0.63	.05	0.200	0.800	41

P_1	P_2	rel. difference	$\alpha/2$	β	power	n
0.6	0.9	-0.75	.025	0.200	0.800	31
0.6	0.89	-0.73	.025	0.200	0.800	34
0.6	0.88	-0.70	.025	0.200	0.800	37
0.6	0.86	-0.65	.025	0.200	0.800	45
0.6	0.85	-0.63	.025	0.200	0.800	51

PRELIMINARY DATA: Kim PJ, Attinger CE, Steinberg JS, Evans KK, Powers KA, Hung RW, Smith JR, Rocha ZM, Lavery L. The impact of negative-pressure wound therapy with instillation compared with standard negative-pressure wound therapy: a retrospective, historical, cohort, controlled study. *Plast Reconstr Surg.* 2014 Mar;133(3):709-16.

This study shows that NPWT with two different doses of Prontosan irrigation solution decreases the number of surgeries, length of hospitalization, and increases the proportion of wounds that are closed compared to “traditional NPWT”. We conducted a retrospective study of hospitalized patients with infected lower extremity wounds that received NPWT without irrigation (n=74), NPWT with irrigation with polyhexanide biguanide (PHMB) with a 6 minutes dwell time (n=34), and NPWT with irrigation with polyhexanide biguanide (PHMB) with a 20 minute dwell time (n=34). The proportion of wounds that were surgically closed was significantly higher, and the number of surgeries was significantly less in patients that received NPWT with 6 minutes of irrigation compared to standard NPWT without irrigation. Similar trends were seen with NPWT with 20 minutes of irrigation.

Table 1	NPWT n=74	NPWT 6 minute irrigation n=34	NPWT 20 minute irrigation n=34
Number of Surgeries	3.0 ± 0.9	2.4 ± 0.9 p=0.04	2.6 ± 0.9 p=0.003
Length of Stay (days)	14.9 ± 9.2	11.9 ± 7.8 p=0.10	11.4 ± 5.1 p=0.03
Time to Final Surgical Procedure	9.23 ± 5.2	7.8 ± 5.2 p=0.04	7.5 ± 3.1 p=0.002
Percent Closed	62%	94% p<0.001	80% p=0.08

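### The 80% power tabulated for the irrigation comparison rests on before-discharge closure rates with antiseptic instillation, and is unsupported for this trial's irrigant, time window, endpoint and test

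*Combined protocol and SAP*

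**What the plan says.** The Sample Size Justification gives the source rates: "The proportion of subjects with closed wound was 62% using traditional KCI NPWT and 94% using NPWT with periodic irrigations with Prontosan". From these, "we estimated 85-90% wound closure with NPWT with irrigation and 60% wound closure with NPWT without irrigation". It calls this the previous justification but offers no other. The printed two-proportion formula feeds two tables for 60% against 90, 89, 88, 86 and 85%. Every row shows power 0.800, with 25–41 per group at two-sided 10% and 31–51 at two-sided 5%.

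Preliminary Studies, Study 2 describes the same cohort and names the outcome: "Percentage of wounds closed before discharge". The table in the sample size section gives mean stays of 14.9, 11.9 and 11.4 days. Both irrigation arms received PHMB, with a 6- or 20-minute dwell; 94% and 80% closed, against 62% without irrigation.

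For this trial:
- **Irrigation:** the device table specifies "125mm Hg with continuous irrigation, normal saline 15 cc/hr". Home Health Visits states that NPWT at home has no irrigation.
- **Window:** Therapy Administration sets the individual evaluation endpoint at 4 weeks or readiness for surgical closure, if earlier, but also says "subjects may be followed up to the full 12 weeks, and closure may occur anywhere inbetween".
- **Primary endpoint:** Objective 1B names reduction in wound volume.
- **Primary method:** Survival Analyses Models names Kaplan-Meier estimates and a log-rank test.
- **Size:** 90 patients randomized 1:1:1, so 30 per arm. No dropout allowance is stated.

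**The concern.** The planning rates and the trial differ in four ways, and the plan bridges none of them: the irrigant and how it is delivered, the time over which closure is counted, the endpoint, and the test. The cohort was also limited to hospitalized patients with infected lower-extremity wounds, while the inclusion criteria here cover many wound types.

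Objective 1B carries a directional hypothesis that irrigation heals more wounds, and the only power figure a reader can attach to it is 80%. If irrigation shows no significant advantage, that figure invites the reading that a worthwhile effect has been ruled out. The data may not allow that conclusion.

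**Working it through.** **1. Reproduce the plan's figures.** The printed formula is n = [z(α/2)·√(2P(1−P)) + z(β)·√(P1(1−P1) + P2(1−P2))]² / (P1−P2)², with P the mean of P1 and P2.

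For 60% against 90%: P = 0.75, √0.375 = 0.612, √(0.24 + 0.09) = 0.574.
- Two-sided 5%: (1.960 × 0.612 + 0.842 × 0.574)² / 0.09 = 31.5 (plan: 31).
- Two-sided 10%: (1.645 × 0.612 + 0.842 × 0.574)² / 0.09 = 24.7 (plan: 25).

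Rounded up to whole patients, all ten rows agree within 2. The 85% rows come to 38.4 and 48.9, against 41 and 51 printed. The arithmetic is not the problem.

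**2. Power of the actual 30 per arm.** Inverting the same formula: power = Φ{[√30·|P1−P2| − z(α/2)·√(2P(1−P))] / √(P1(1−P1) + P2(1−P2))}. For 60% against 90% at 5% this is Φ[(1.643 − 1.200)/0.574] = Φ(0.77) = 78%.

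| Closure, no irrigation vs irrigation | Power, 5% | Power, 10% |
|---|---|---|
| 60 vs 90 | 78% | 87% |
| 60 vs 89 | 74% | 84% |
| 60 vs 88 | 71% | 81% |
| 60 vs 86 | 63% | 74% |
| 60 vs 85 | 59% | 71% |
| 62 vs 80 (cohort, 20-minute arm) | 33% | 46% |

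These figures use only rates printed in the protocol. With 30 per arm, 80% is reached in no 5% row, and at 10% only where irrigation closure is 88% or more. At 62% against 80%, 80% power would need 99 per arm (5%) or 78 (10%).

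**3. The named test over a longer window (assumed rates).** Take the hazard ratio implied by each pair, HR = ln(1−P2)/ln(1−P1), and assume it stays constant. For an assumed control closure c, irrigation closure is 1 − (1−c)^HR, the number of closures is D = 30 × (sum of the two proportions), and log-rank power is Φ[(√D/2)·ln HR − 1.960] at two-sided 5%.

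Example: 60 vs 90 gives HR = ln 0.10/ln 0.40 = 2.51. With c = 0.70, irrigation closure is 0.951, D = 49.5 and power is 90%.

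| Source of HR | HR | Log-rank power, control closure 70–90% |
|---|---|---|
| 60 vs 90 | 2.51 | 90–94% |
| 60 vs 85 | 2.07 | 72–78% |
| 62 vs 80 | 1.66 | 41–48% |

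The control range of 70–90% is an assumption; the documents give no such rate.

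**4. Wound volume.** No expected difference or standard deviation for volume appears anywhere, so power for the declared primary endpoint cannot be computed.

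**The case against.** The strongest defence has four parts.

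*The limits are largely disclosed.* The section says that no data exist for this device, that one purpose is to gather data to power a larger multicentre study, and that the source used Prontosan. It prints the 80% arm with p = 0.08, and it shades 94% down to 85–90%. This stands, and it makes the point a matter of restating rather than redesigning. But no replacement calculation follows, and 0.800 is still printed in every row.

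*A longer window need not reduce power.* This also stands. A reader might infer that a later cut-off lifts control closure to 70, 75 or 80% while irrigation stays at 90%, so that power falls to 49, 33 or 19% at 5%. The documents do not support that: they give no such control rates, and a longer window would raise both arms. If HR 2.51 carried forward, the pairs would be 70/95, 75/97 and 80/98, with two-proportion power of 74, 70 and 63%, and the log-rank test would do better still. Against this, irrigation stops at discharge, after which both PRO arms receive the same therapy, so a constant hazard ratio is itself doubtful.

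*Control closure of 60% is not impossible here.* Also fair. The protocol expects most wounds to be ready by 4 weeks and allows some not to be ready at 12, which is compatible with 60%.

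*The preliminary experiment does not show that irrigation fails.* Irrigation "improved wound healing rates over control treated wounds, however did not differ from NPWT alone", but that was a porcine model of inoculated wounds. Saline and PHMB each reduced bioburden beyond NPWT alone, which softens the irrigant objection. It supplies no closure rate for patients treated with saline.

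**Conclusion.** The concern holds as a question of support. The tabulated 80% describes a two-proportion test on closure before discharge, with the irrigated group receiving antiseptic instillation, and it cannot be carried to this trial's irrigation contrast. The documents do not show that true power is lower; it could lie on either side of 80%.

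One part needs no outside assumption. On the plan's own rates and formula, 30 evaluable patients per arm give 59–78% power at two-sided 5% and 71–87% at 10%, and the cohort's second irrigation arm gives 33% and 46%. Any dropout would lower these. The log-rank figures also rest on proportional hazards and on assumed control closure of 70–90%.

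**What to change.** Keep 90 patients and rewrite the sample size section:

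1. State that the planning rates derive from before-discharge closure in a retrospective inpatient cohort, with PHMB instillation in the irrigated arms.
2. Replace the two 0.800 tables with the power of 30 per arm over 60% against 85–90% and for 62% against 80%, for both the two-proportion and log-rank tests. Mark longer-window rates as assumptions and let both arms rise.
3. State that wound volume, the declared primary endpoint, is not powered.
4. Report the irrigation contrast as an estimated difference with a confidence interval, intended to size the later multicentre trial.
5. Reconcile the 4-week and 12-week evaluation passages so that the closure window is defined once.

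The cost is redrafting and less favourable printed power at 5% for the two-proportion test. No patients or visits are added.
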